7.1.2 Summarization by Visit

Data summarized by study visit will be based on the nominal, scheduled visit from the eCRF or tablet. Analysis visits will be labelled as Baseline or Day 1, Day 4, Day 14, and Day 28 in all table summaries.

Data collected for the last subject treatment visit completed will be summarized separately for:

- The scheduled Day 14 (End of Treatment) visit for those subjects who complete the scheduled end of study visit, per protocol. This summary will be labeled as “Day 14” in the analysis.
- The last visit completed on-study, combining data collected for subjects who complete the Day 14 (End of Treatment) visit as well as the early termination (ET) visit for those subjects who discontinue the study early. This summary will be labeled as “Day 14/ET” in the analysis.

For assessments collected daily on the smartphone/trial application, visits will be summarized based on the study day relative to the date of treatment start for all data. However, statistical analyses will be conducted using Day 1 through 14 observations only.

Data collected at unscheduled visits will not be included in by-visit summaries, but will be considered when endpoint derivations potentially include multiple visits (e.g., determination of baseline value, determination of worst post-baseline value, etc.). All data will be included in subject listings.

7.1.3 Baseline Value

For analyses listed in this SAP, the baseline value is defined as the last measurement reported prior to the first dose of study drug, unless otherwise noted.

7.1.4 Data Handling Rules

Unless otherwise noted, values reported as greater than or less than some quantifiable limit (e.g., “< 1.0”) will be summarized with the sign suppressed in summary tables and figures, using the numeric value reported. Data will display on subject listings to include the sign.

If duplicate post-baseline subject reported outcomes are present for a study day and/or time point, the earlier of the duplicates recorded will be used for analysis. Duplicate data that is not used in table summaries for efficacy endpoints will be flagged with an asterisk in their respective listings.

7.1.5 Standard Calculations

Where appropriate, the calculated study day of each assessment or event will be presented with the assessment or event date on subject data listings, where study day will be determined as:

- The assessment/event date minus the date of first dose of study drug, if the assessment/event date is prior to the date of first dose; and
- The assessment/event date minus the date of first dose of study drug, plus one, if the assessment/event date is on or after the date of first dose.

Other variables requiring calculations will be derived using the following formulas:

- **Days:** A duration between two dates expressed in days will be calculated using the following conventions:
 - Later date – earlier date + 1, if the earlier date is on or after the date of first dose of study drug; or
 - Later date – earlier date, if the earlier date is prior to the date of first dose of study drug.
- **Change from Baseline:** Change from baseline will be calculated as the post-baseline value minus the baseline value.

7.2 Analysis Populations

The analysis populations are defined as follows:

- **Intent-to-Treat (ITT) Population:** All randomized subjects who receive any amount of study drug. This population will be used as the primary analysis population for all efficacy endpoints. Subjects will be included in this population based on their randomized treatment assignment.
- **Safety Population:** All subjects who receive any amount of study drug. This population will be used for all summaries of safety data. Subjects will be included in this population based on the highest dose level received.
- **Per-Protocol (PP) Population:** All randomized subjects who complete the study treatment period with a minimum of 12 days of treatment and have no significant protocol violations that would affect the efficacy analyses. The PP Population will be determined prior to database lock and will be used for sensitivity analyses on the primary and select secondary endpoints. Subjects with major protocol deviations will be excluded from the efficacy analyses. See section 7.3.2 for further details on protocol deviations.

Data summaries to be presented on both the Safety Population and the ITT Population will only be produced on both analysis sets if there is a difference in the population groups.

7.3 Study Subjects

7.3.1 *Disposition of Subjects*

Subject disposition will be summarized for all randomized subjects by tolperisone dose group/placebo and total tolperisone treated subjects combined. Summaries will include the number and percentage of subjects in each analysis population, subjects completing a minimum of 12 days of treatment, subjects completing the study, and those discontinuing the study early by the primary reason for discontinuation. Subject disposition will also be summarized separately for each study site.

A data listing of study disposition will be presented by treatment group, site, and subject.

7.3.2 *Protocol Deviations*

Major protocol deviations will be summarized by tolperisone dose group/placebo and for total tolperisone treated subjects combined for the ITT Population. Major protocol deviations are protocol deviations captured on-study that are deemed by the Sponsor to potentially impact the efficacy or safety conclusions of the study. Subjects with major protocol deviations will be excluded from the PP Population for analysis.

All major protocol deviations will be determined and appropriately categorized prior to database lock and prior to breaking the blind of the treatment group assignments. The number and percentage of subjects with any major protocol violations as well as the number and percentage of subjects with violations within each category will be presented. Anticipated protocol deviation categories include inclusion/exclusion criteria, investigation product, prohibited concomitant medications, visit schedule, procedures/tests, SAEs not reported/reported late, and other.

A data listing of patients with all protocol deviations will be presented by treatment group, site, subject, and date of deviation. In addition to protocol violations, a data listing of informed consent and eligibility criteria will be presented.

7.3.3 *Enrollment*

A data listing of the randomization scheme and treatment codes will be presented.

7.4 Efficacy Evaluation

7.4.1 *Datasets Analyzed*

All efficacy summaries will be based on the ITT Population; select efficacy summaries will also be produced on the PP Population. A data listing of subjects excluded from the ITT or PP Population, to include the reason for exclusion, will be presented.

7.4.2 Demographic and Other Baseline Characteristics

Demographic variables including age, sex, ethnicity and race will be summarized by tolperisone dose group/placebo and for total tolperisone treated subjects combined for the Safety, ITT, and PP Populations. Age will be summarized using descriptive statistics. Frequency counts and percentages of subjects by age category, sex, ethnicity, and race categories will be summarized.

Baseline characteristics including CYP450 2D6 polymorphism, smoking history, height, weight, and body mass index (BMI) will be summarized by tolperisone dose group/placebo and for total tolperisone treated subjects combined for the Safety, ITT, and PP Populations.

Height, weight, and BMI at baseline will be summarized using descriptive statistics. Genotype and smoking history will be summarized with frequency counts and percentages.

Genotype results will also be presented in a by-subject data listing.

7.4.3 Measurements of Treatment Compliance

Compliance to the study treatment regimen will be determined as the total number of doses received divided by the expected number of doses received, multiplied by 100.

The total number of doses received will be determined based on the number of protocol-required doses (i.e. 42 doses) minus the number of tablets returned as reported in the eCRF.

Subjects are not expected to receive all three doses on the first (Day 1) and last (EOT/ET) day of dosing. The expected number of doses will be derived as outlined in [Table 4](#).

Table 4 Expected Number of Doses

Row	First Dose Time	Doses expected Day 1	Last Dose Time	Doses expected EOS/ET	Doses expected Day 1 & EOS/ET	Doses not expected Day 1 & EOS/ET
1	12am-12pm	3	12am-12pm	1	4	2
2	12am-12pm	3	12pm-6pm	2	5	1
3	12am-12pm	3	6pm-12am	3	6	0
4	12pm-6pm	2	12am-12pm	1	3	3
5	12pm-6pm	2	12pm-6pm	2	4	2
6	12pm-6pm	2	6pm-12am	3	5	1
7	6pm-12am	1	12am-12pm	1	2	4
8	6pm-12am	1	12pm-6pm	2	3	3
9	6pm-12am	1	6pm-12am	3	4	2

Complete 14 day TID dosing

If the first dose of study drug occurs in the morning (between 12am and 12pm) and the last dose occurs in the evening (between 6pm and 12am) then the expected number of doses should be calculated as $3 \times (\text{date of last dose} - \text{the date of first dose} + 1)$ (Table 4: Row 3).

Partial dosing on First and Last Day of Dosing

If the first dose occurs in the afternoon (between 12pm and 6pm) and last dose occurs in the morning (between 12am and 12pm), the expected number of doses should be calculated as $3 \times (\text{date of last dose} - \text{the date of first dose} + 1) - 3$ [doses not expected on first & last days] to account for the fewer number of expected doses on the first and last days of treatment (Table 4: Row 4).

For subjects with non-missing date of last dose, but missing time of last dose on the CRF, if the date of last dose on the CRF is equivalent to the last date of entry on the subject eDiary, the corresponding eDiary time point (AM, MID, PM) will be used for compliance calculations. Otherwise, if the last dose date on the CRF and date of latest entry on the eDiary are not equivalent, subjects will be imputed to have received 1 dose on the given CRF date of last dose.

Dosing compliance will be summarized using descriptive statistics, by treatment group, based on the Safety Population. The number and percentages of subjects who are < 80% compliant and $\geq 80\%$ compliant within each treatment group will be summarized. A data listing of subject compliance will also be presented.

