10. STUDY DESIGN

10.1. Summary of Study Design

This is a double-blind, randomized, placebo-controlled, parallel group study of the efficacy and safety of multiple doses of tolperisone administered TID in approximately 400 male and female subjects experiencing back pain due to or associated with muscle spasm. The tolperisone groups consist of dose levels of 150, 300, 450, and 600 mg administered TID in doses of 50, 100, 150, or 200 mg for 14 days, with a visit at 28 days as follow-up. Subjects randomized to the placebo group will receive matching placebo tablets TID for 14 days. Subject participation will be approximately 4 weeks.

Subjects will be screened for eligibility for participation in the study at Screening/Baseline Visit 1 (Day 1) after reviewing and signing the informed consent form. Subjects meeting all inclusion/exclusion criteria will then be randomized into the study (Day 1) and begin dosing this same day. If needed, screening assessments may be completed up to 3 days prior to Day 1 (first dose) as described below.

It is highly recommended to complete all screening and baseline assessments on the same day the subject presents at the site due to their acute pain relief needs. However, to accommodate real world logistical issues and time constraints of either the subject or site, the site has the flexibility to allow completion of screening assessments within 3 days (-3 days) prior to Day 1 baseline assessments, deployment of study-provisioned smartphone/download of trial application on subject's smartphone, randomization, and first dose (in that order).

After completing all screening and baseline assessments by/on Day 1, subjects will receive all study drug and rescue medication (acetaminophen 500 mg) and will be instructed to begin taking their study drug that same day. Depending on the time of their clinic visit, they should be instructed to begin dosing with either the midday dose (12-2 pm) or the evening dose (6-8 pm). Subjects will be instructed to continue taking study drug TID through Day 14 and complete dosing diary and daily ePRO assessments.

Subjects will return to the clinic to complete the procedures listed in the Schedule of Procedures on Day 4 (± 1 day; Visit 2) and Day 14 (+1 day, End of Treatment [EOT] visit, Visit 3). Subjects must also return to the clinic for a follow-up visit on Day 28 (+3 days, 2-week follow-up visit, Visit 4).

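### Expected doses in the SAP compliance formula end at the last dose taken, so a subject who stops study drug early but attends Visit 3 can be classed as at least 80% compliant

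*SAP*

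**What the plan says.** SAP 7.4.3 defines the measure as a percentage: "Compliance to the study treatment regimen will be determined as the total number of doses received divided by the expected number of doses received, multiplied" (the factor is 100). The numerator is the "number of protocol-required doses (i.e. 42 doses) minus the number of tablets returned as reported in the eCRF".

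The denominator is three times the number of calendar days from first to last dose, less an allowance for partial first and last days taken from Table 4. The worked text for an afternoon start reads "and last dose occurs in the morning (between 12am and 12pm), the expected number of doses should be calculated as" three times that span, minus three. Table 4 is keyed to the clock time of the last dose. If that time is missing and the CRF and eDiary dates disagree, "subjects will be imputed to have received 1 dose on the given CRF date of last dose".

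The same section describes the last day differently: "Subjects are not expected to receive all three doses on the first (Day 1) and last (EOT/ET) day of dosing". The Table 4 columns are likewise headed EOS/ET.

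The result is summarised descriptively by arm in the Safety Population, with a split at 80%: "The number and percentages of subjects who are < 80% compliant and" those at or above it. The regimen being measured is set in Protocol 10.1: "Subjects will be instructed to continue taking study drug TID through Day 14".

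**The concern.** The labels assume that the last dose falls at the end-of-treatment or early-termination visit. The formula does not require this. For a subject who stops tablets earlier and stays in the study, the two readings differ, and no rule in 7.4.3 covers the case. Followed as written, the window closes when the subject stops. Doses missed in the middle count against the subject; doses missed from some day onward do not.

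At stake is the accuracy of one table. A subject who took less than half the course can appear in the group at or above 80%. If such stopping differed between dose arms, neither the compliance percentage nor the 80% split would show it.

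**Working it through.** **Inputs.** All are from SAP 7.4.3 unless stated.
- Doses received = 42 − tablets returned.
- Expected doses = 3 × (date of last dose − date of first dose + 1) − doses not expected on the first and last days.
- First-day doses expected: 3 (morning start), 2 (midday), 1 (evening). Last-day doses expected: 1 (last dose in the morning), 2 (afternoon), 3 (evening). Doses not expected = 6 − (first-day + last-day).
- First dose on Day 1 is midday or evening (Protocol 10.1).

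**Reproducing the plan's figures.** First-day plus last-day doses give, for Rows 1 to 9, expected/not expected of 4/2, 5/1, 6/0, 3/3, 4/2, 5/1, 2/4, 3/3 and 4/2. All nine rows match Table 4. Row 3 over 14 days gives 3 × 14 − 0 = 42, matching the 42 required doses.

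**An early stop followed by Visit 3 on the morning of Day 14.** The subject starts on the evening of Day 1, takes every dose until a morning stop (Row 7, subtract 4) and returns all unused tablets.

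| Last dose | Taken | Expected as written | Score | Expected to Visit 3 | Score |
|---|---|---|---|---|---|
| Day 7 morning | 1 + 15 + 1 = 17 | 3 × 7 − 4 = 17 | 100% | 3 × 14 − 4 = 38 | 17/38 = 45% |
| Day 10 morning | 1 + 24 + 1 = 26 | 3 × 10 − 4 = 26 | 100% | 38 | 26/38 = 68% |

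**Other patterns.**
- For a Day 7 stop after full adherence, all nine first/last time combinations score exactly 100% as written. With a midday or evening start and the window run to Day 14, they score 42.5% to 51.3%, depending on start time, stop time and how many doses are expected on Day 14.
- Midday start, last dose on the evening of Day 7: 20 taken, 3 × 7 − 1 = 20 expected. Four further missed doses before the stop still give 16/20 = 80%, counted as at least 80%.
- One tablet on Day 1 and none after: 1/1 = 100%.
- If the time of last dose is missing and the one-dose imputation applies to the 20-tablet subject, expected is 3 × 7 − 3 = 18 and the score is 20/18 = 111%.
- Where the classification changes (midday start, full adherence, evening stop): up to Day 10 if one dose is expected on Day 14 (29/39 = 74%; Day 11 gives 32/39 = 82%), or up to Day 11 if three are expected (32/41 = 78%; Day 12 gives 35/41 = 85%).

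**Arm-level illustration.** The documents give no rate of early stopping. If 10% or 20% of an 80-subject arm followed the Day 7 pattern (assumed), 8 or 16 subjects would be placed on the wrong side of 80%. Mean compliance would be overstated by 0.10 × (1 − 17/38) = 5.5 points or 0.20 × (1 − 17/38) = 11 points.

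**The case against.** The strongest reply is that other planned outputs show what this percentage misses. SAP 7.5.1 tabulates total dose received in mg, based on tablets returned, and duration of exposure. In the 600 mg/day arm the Day 7 stopper shows 17 × 200 = 3,400 mg against 38 × 200 = 7,600 mg. If 20% of that arm stopped so, mean total dose would fall to 7,600 − 0.20 × 4,200 = 6,760 mg, about 11% lower. SAP 7.3.1 counts subjects completing 12 days of treatment. The Per-Protocol Population (SAP 7.2) separately requires 12 days, so both examples above are excluded from it. The 80% split defines no population and enters no test. Sites also review the eDiary portal and check returned drug at Visits 2 and 3 (Protocol 11.2), and non-compliance is a listed reason for withdrawal (Protocol 9.3). Finally, compliance over the days actually dosed is a coherent quantity when reported beside duration.

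Most of this stands and limits the consequence. A reader might infer that the rule could hide a flat Day 14 dose trend caused by stopping, or that compliance stays near 100% however many subjects stop. The documents do not support either inference. Total dose and duration would reveal the shortfall, and the score stays high only for subjects who were largely adherent before stopping. Nor do the documents show that stopping tablets while still attending Visit 3 is common.

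The reply does not make the percentage or the classification right. The section says it measures compliance with the study regimen, it labels the last day as the visit, and its formula uses another date. Average dose in 7.5.1 gives little help, because its divisor also ends at the last dose.

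**Conclusion.** The point holds as a minor correction. For subjects who stop study drug before the EOT/ET visit, SAP 7.4.3 as written cannot count the doses omitted afterwards, and it conflicts with its own EOT/ET labels. The size in the worked cases is 100% against 45% (Day 7 morning stop) and 100% against 68% (Day 10 morning stop), each moving the subject across the 80% line. These figures assume an evening start, every dose taken until the stop, return of all unused tablets and Visit 3 on Day 14. Earlier missed doses lower the score; unreturned tablets raise it.

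The effect stops at the descriptive compliance percentage and the table split at 80%. The primary ITT analysis, the Per-Protocol definition and the exposure tables are unaffected.

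**What to change.** In SAP 7.4.3 and Table 4:
- End the expected-dose window at the later of (a) the date of last dose and (b) the EOT/ET visit date or Day 14, whichever of those two is earlier.
- Where the last dose falls on the end date, keep the Table 4 allowance. Where it precedes the end date, expect one dose on that date if it is the visit day, in line with the SAP's one-dose imputation, and three if it is Day 14 with a Day 15 visit.
- Cap expected doses at 42.
- Use this figure for the 80% table, labelled as compliance over the period on study. Keep the present ratio as a second line, labelled as compliance while taking study drug.

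The rule uses dates only, since the documents do not show that the clock time of Visit 3 is captured. Letting the window follow a later last dose avoids a new error. An evening starter who takes every dose has used 1 + 39 = 40 tablets by Day 14; one more on the morning of Day 15 would score 41/40 under a plain Day 14 cut-off, but scores 41/(3 × 15 − 4) = 41/41 here. With a Day 15 visit, the Day 7 morning stopper scores 17/(1 + 36 + 3) = 17/40 = 42.5%.

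One limit remains. A subject who stops and attends an early-termination visit on Day 7 still scores about 100%, because the figure covers time on study and not the full 14-day regimen. For early withdrawals the table should direct the reader to duration of exposure and total dose.

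The cost is a change of wording and a small programming change, using visit and dose dates already collected, and stated compliance that is slightly less favourable.

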7.4.4 Primary Efficacy Endpoint Analysis Methods

The primary efficacy endpoint is NRS subject-rated pain “right now” due to acute back spasm on Day 14 for all subjects in the ITT population. This analysis will be performed using a linear test of trend across all tolperisone doses.

The null and alternate hypotheses to be tested are:

H₀: There is no significant trend in NRS rating of pain “right now” across dose groups

H₁: There is significant trend in NRS rating of pain “right now” across dose groups

The linear test of trend will be performed using a mixed effect model for repeated measures (MMRM) using an unstructured covariance matrix to model within-patient errors. However, if the computational algorithm fails to converge, other covariance structures will be evaluated (e.g., compound symmetry). The covariance structure converging to the best fit, as determined by Akaike’s information criterion, will be used. The Kenward and Roger method will be used to calculate the denominator degrees of freedom for the test of fixed effects. Based on this model, the hypothesis test described above will be tested using a two-sided test at the $\alpha=0.05$ level of significance.

The response variable will be the observed NRS rating of pain “right now”. The observed value on Day 14 is the primary time point of interest. The model will include factors for treatment group (5 levels: placebo, 150 mg/day, 300 mg/day, 450 mg/day and 600 mg/day) and visit (three levels: Day 1/Baseline, Day 4, and Day 14) as fixed effects, the treatment by visit interaction, and the baseline NRS rating as a covariate. The primary analysis will be based on all available data without imputation. Day 14 will reflect subjects that have completed the scheduled Day 14 (Visit 3). Subjects discontinuing the study may be analyzed as part of the sensitivity analysis using data imputation methods (LOCF and Multiple Imputation) to address missing data.

The observed NRS rating and change from baseline values will be presented using descriptive statistics for each treatment group by visit. The p-value for the overall test of trend on Day 14 will be presented. The pairwise least-square mean (LSM) estimates and least-square mean differences (LSMD) for each tolperisone dose level versus placebo will also be presented with 95% confidence intervals of the LSMD and associated p-values for the Day 14 visit observed values.

A plot of NRS subject rating of pain right now across study days will be presented.

